4. IDENTIFICATION AND DESCRIPTION OF THE INVESTIGATIONAL DEVICE

4.1 Summary description of the investigational device and its intended purpose

The ARGOS-IO system was developed for the wireless, contactless measurement of the hydrostatic pressure of the aqueous humor (IOP, intraocular pressure) in patients with diagnosed glaucoma, or

	Clinical Investigation Plan ARGOS-02	Revision C
		Page 32 of 106

elevated or instable IOP that places them at a risk of ocular damage and loss of visual acuity. It is made up of four components: the ARGOS-IO implant, the external hand-held Mesograph reading device, the implant injector and the Multiline Connector.

The ARGOS-IO implant is comprised of a micro-electromechanical system application specific integrated circuit (ASIC) bound to a micro-coil of gold and encapsulated in a silicone-rubber material that has been widely used for intraocular lenses. It is intended to be implanted during cataract surgery, and to remain in place indefinitely. The implant is introduced into the area between the intraocular lens and the iris (ciliary sulcus) using standard procedures that employ an implant injector similar to those commonly used to insert IOLs.

Activation of the Mesograph reading device in the near vicinity of the eye establishes an inductive current between it and the micro-coil, thereby supplying the ASIC with power and permitting data transmission. Pressure-sensor cells and an A/D converter incorporated in the ASIC measure IOP directly and transmit the digitized data to the reader. When connected to the reader at the site or the patient's home, the Multiline Connector uploads the data recorded by the reader to a secure dedicated data base that can be accessed remotely by the Investigator. Data is redundantly stored in non-volatile memory inside the reader device, preventing data loss in case of an error.

Because the sensors are implanted in the eye, the ARGOS-IO pressure sensor measures IOP directly, without interference from corneal properties or due to operator skill. It enables numerous IOP measurements daily, providing a complete IOP profile for the entire interval between office visits, and allowing timely detection of both peaks due to patient activities and circadian rhythms and trends due to disease progression. It also permits easy patient self-monitoring, thereby providing patients immediate feedback on their IOP, which in turn should encourage adherence to the treatment regimen.

	Clinical Investigation Plan ARGOS-02	Revision C <hr/> Page 33 of 106
---	---	------------------------------------

4.2 Description of the investigational device including any materials that will be in contact with tissues or body fluids

The ASIC and micro-coil components of the implant are hermetically encapsulated in a biocompatible silicone-rubber material (Nusil MED-6820) commonly used for ophthalmic implants. This layer of material:

- Forms a biocompatible, soft and atraumatic surface of the implant in order to avoid trauma to the tissues surrounding the implant
- Prevents and protects the patient from substances being washed out from the electronic module and leaking into the aqueous humor
- Provides a hermetic leak-proof seal around the electronic module, protecting it from the electrolytes and water contained in aqueous humor.

In the event that the silicone coating were to become breached the patient may indirectly come into contact with the materials of the ASIC and the micro-coil as well. The sponsor commissioned a detailed risk assessment performed by NAMSA Advisory Services, Atlanta, USA to determine if these materials would pose any risk of an adverse biological effect to the patient. The materials under investigation comprised silicon, silicon dioxide, silicon nitride, gold, and traces of aluminum, titanium, phosphorus, arsenic, borium, polyimide and tungsten-titanium. The report states that all materials have been used previously within the eye and are considered to pose little if any risk (Cao, M, 2010).

The implant is required to fit into the ciliary sulcus which is a relatively tight area in a phakic eye, but is deeper in the pseudophakic eye. The implant shape and profile is designed to:

- Be folded prior to implantation and to be manipulated through a relatively tight up to 5 mm corneo-scleral tunnel
- Not block the optical axis of the eye
- Avoid the IOL, although it may be in direct contact with parts of it
- Have a minimum profile and thickness
- Have rounded edges in order to avoid trauma when in long term contact with the surrounding tissue.

The implant contains four haptics to maintain positional stability. In addition, the two haptics on either side of the ASIC act as a spacer to prevent the ASIC from being pressed into the surrounding tissue. Two flattened allantoic protrusions running from the bottom middle to the ASIC on the posterior

	Clinical Investigation Plan ARGOS-02	Revision C
		Page 34 of 106

surface of the ring serve to facilitate unfolding of the implant after insertion into the eye, as well as to decrease force exerted on the ASIC by the ocular structures.

The implant is packaged in multiple layers conforming to EN ISO 11607-1:2006 and then sterilized with ethylene oxide.

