4.6 Necessary training and experience requirements

It is assured that ophthalmic surgeons performing the surgery will be adequately trained on the ARGOS-IO pressure sensor implantation. Site personnel responsible for device handling including accountability, storage and shipment procedures will be trained during the initiation visit. If new site personnel are assigned during the study, they will be trained by the principal investigator or the monitor.

Surgical implantation

- Only specially trained ophthalmic surgeons may perform the implantation. These surgeons must be made familiar with the handling and implantation of the ARGOS-IO pressure sensor either by special training through Sponsor representatives or by consultation of the User Manual, provided as a separate document.

 Implandata Ophthalmic Products GmbH	Clinical Investigation Plan ARGOS-02	Revision C
		Page 36 of 106

Intraocular pressure measurement using the Mesograph Reading Device:

- Intraocular pressure (IOP) measurement may be carried out by any trained individual including patients and assistants. Health care professionals will be trained by sponsor representatives or their delegates. Trial staff will instruct patients on the use of the reading device for IOP self-measurement at home at visit 05. Patients will also be given separate written handling instructions provided by the Sponsor.

Setup of reading device, downloading of measurement data:

- Only specially trained site personnel may set up the reading device or download data from it. Special attention must be paid to maintaining data protection in this connection. Training will be provided by Sponsor representatives.

Evaluation of data:

- The data obtained by the ARGOS-IO system measurement will only be used for the evaluation of the trial outcome. The ophthalmologist will use only the IOP measurements made with GAT for diagnosis, therapeutic assessments and decisions about additional medical treatments.

4.7 Description of any specific medical or surgical procedures involved in the use of the investigational device.

Ophthalmic surgeons should perform the cataract surgery according to their local routine working procedures for cataract surgery. The implantation of the ARGOS-IO pressure sensor should occur according to the training received prior to any surgery given by the Sponsor.

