8.1.2 Description of the measures to be taken to minimize or avoid bias

No randomization and blinding/masking procedures will be used in this study. To avoid bias resulting from prior knowledge of the IOP value from the ARGOS-IO system on the measurement obtained with GAT, GAT will be used first.

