8.4.4.15 Intraocular pressure (IOP) measurement

Intraocular pressure (IOP) will be measured using two techniques. Goldmann Applanation Tonometry (GAT) will be performed in the clinic at every visit. Beginning at V05, IOP measurement will also be performed with the ARGOS-IO system, both by site personnel at clinic visits and by the patient at home between visits. Only GAT will be used to guide any treatment decisions. The GAT must be performed by preferably one or at maximum two dedicated investigators at each site to reduce potential bias.

IOP measurement in the clinic

Each IOP measurement will be conducted as a series of 1x GAT followed by 3x ARGOS-IO system, except for Visits SC through V04 when only GAT will be used. When series of measurements are made, the GAT must always be used first to avoid operator bias. There should be no more than 10 minutes between the GAT measurement and the first of the ARGOS-IO system measurements in a series, and at least 60 minutes will lie between the last measurement with the ARGOS-IO system in one series and the GAT of the next.

IOP will be measured at least two times at every visit, preferably at the beginning and end of the visit. At Visits 05, 07, 09 and 11, IOP will be measured 4 times. Again, effort should be made to ensure there are at least 60 minutes between measurement series.

ARGOS-IO system measurement by the patient at home

At V05 (D30), after detailed instruction in their use, the patients will receive an individual Mesograph reading device and the Multiline Connector to perform self-tonometry at home. The patients will be requested to perform at least 4 IOP measurements with the Mesograph daily, evenly spread throughout the day. They will also be requested to connect the reader to the Multiline Connector on a regular basis to transfer the recorded IOP data directly into the secure database. No manual recording of data by the patient will be required.

Patients shall be instructed to bring the Mesograph reading device to every visit to permit site staff to check its functionality and to delete the measured IOP data from the device. The device routinely stores up to 3.000 measurements.

 Implandata Ophthalmic Products GmbH	Clinical Investigation Plan ARGOS-02	Revision C <hr/> Page 75 of 106
--	---	------------------------------------

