¹⁴ At visits 5, 7, 9 and 11 at least 4 series of IOP measurements will be performed, with at least 60 minutes between the last measurement in one series and the first measurement in the next.

¹⁵ All patients will receive a MESOGRAPH reading device at Visit 05 in order to measure the IOP daily at home. Measurements shall be taken at least 4 times per day (morning, noon, afternoon, evening). The MESOGRAPH reading device will be connected to an external GSM module, which will transfer the measured value directly to a secure database. Investigators can log into the database in order to track the pressure levels of their patients as required.

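### Investigators who take the GAT readings may view patients' home ARGOS values, so the GAT-first rule does not protect the opening GAT reading at V06 to V09

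*Protocol*

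**What the plan says.** **Access.** CIP 4.1 says that the Multiline Connector "uploads the data recorded by the reader to a secure dedicated data base that can be accessed remotely by the Investigator". That is a device description. The permission that applies during the trial is footnote 15 of CIP Table 6 (section 8.8), repeated in footnote 15 of SAP Table 1: "Investigators can log into the database in order to track the pressure levels of their patients as required". The SAP cites a later CIP revision than the one supplied and still carries this footnote.

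**Home data.** From V05 (day 30) "the patients will receive an individual Mesograph reading device and the Multiline Connector to perform self-tonometry at home" (CIP 8.4.4.15), and "The patients will be requested to perform at least 4 IOP measurements with the Mesograph daily".

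**Who reads GAT.** CIP 8.4.4.15: "The GAT must be performed by preferably one or at maximum two dedicated investigators at each site to reduce potential bias".

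**Safeguards.** CIP 8.1.2 states "No randomization and blinding/masking procedures will be used in this study"; SAP 2.8 agrees. The one measure against knowledge of sensor values is the order within a series. "To avoid bias resulting from prior knowledge of the IOP value from the ARGOS-IO system on the measurement obtained with GAT", GAT is taken before ARGOS. No section keeps the GAT reader out of the database or delays access to it.

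**Endpoint.** Limits of agreement between GAT and ARGOS from V05 through V09 are the primary performance endpoint (CIP 8.1.3.1, SAP 6.3).

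**The concern.** The plan itself names prior knowledge of the ARGOS value as a bias to avoid, and CIP 9.1.4 accepts that GAT is open to operator bias. GAT-first answers this only for the ARGOS readings that follow in the same series. It does nothing about values recorded at home in the preceding weeks, which the people reading GAT are allowed to look up.

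The opening series of a visit is where the ordering rule seems to work, because no ARGOS value has yet been taken that day. From V06 on that protection is incomplete. A comparison of first with later series within a visit would not reveal the problem, since both would be exposed.

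At stake is the quantity the performance objective sets out to estimate. CIP 6.3 reports that ARGOS values ran consistently above GAT in ARGOS-01, and CIP 9.1.4 expects a systematic shift. A reader who knows a patient's usual sensor level may read GAT closer to it, and part of that shift would then be hidden.

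**Working it through.** The plan gives no figure on this point, so the check is a count of scheduled pairs by what the GAT reader could already know.

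**Inputs.** Series per visit from CIP 8.4.3.2; home measurement from V05 (CIP 8.4.4.15); first use of the sensor at day 30 (CIP 5.3); 22 patients, all assumed to have complete data.

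| Visit | Series | First of visit | Later in visit |
|---|---|---|---|
| V05 | 4 | 1 | 3 |
| V06 | 2 | 1 | 1 |
| V07 | 4 | 1 | 3 |
| V08 | 2 | 1 | 1 |
| V09 | 4 | 1 | 3 |
| Total | 16 | 5 | 11 |

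**Classification per patient.**
- V05, first series: no earlier ARGOS value exists. 1 pair.
- V05, later series: same-visit ARGOS values precede GAT, with no home data yet. 3 pairs.
- V06 to V09, later series: same-visit ARGOS values precede GAT whether or not anyone opens the database. 1 + 3 + 1 + 3 = 8 pairs.
- V06 to V09, first series: no same-visit value, but home values can be viewed. 4 pairs.

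Check: 1 + 3 + 8 + 4 = 16. At 22 patients, 16 × 22 = 352 pairs. The pairs newly reached by home access are 4 × 22 = 88, and 88/352 = 25%. In the V10 to V11 window of SAP 6.5 there are 2 + 4 = 6 pairs, of which 2 are first of visit.

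**Amount of home data.** At 4 or more readings a day over the nominal 30 days from V05 to V06, at least 4 × 30 = 120 readings could be on file before the first GAT reading at V06.

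**Direction.** Let b be the mean ARGOS minus GAT difference. Suppose a reader moves GAT toward the sensor by a fraction w of the patient's usual offset on the 4 newly exposed pairs, with the other 12 unchanged. The overall mean difference becomes

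[12b + 4(1 − w)b] / 16 = b(1 − w/4).

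The estimated bias moves toward zero and both limits move with it. The width is less simple. Shrinking the offsets reduces the spread between patients in the exposed pairs, but mixing pulled and unpulled pairs adds some spread within patients. The documents give neither b nor w for this device version, nor the two variance components, so no size can be put on either effect.

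**The case against.** **Exposure is not shown.** Footnote 15 permits log-in as needed; nothing records that a GAT reader used it. CIP 6.1 describes a remote-access platform as something to be developed if the device succeeds. What stands: the finding concerns opportunity only. CIP 6.1 also says that the physician can reach the recorded readings, and a future platform does not withdraw the footnote's permission. The passages should be reconciled.

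**The added information is modest.** Even the four first-of-visit readings follow ARGOS values taken at earlier clinic visits. This stands.

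**Nothing is decided on agreement.** SAP 5.3 makes the performance analysis descriptive, and no acceptance margin is set. This limits the consequence, but limits of agreement that are biased mislead without a test too.

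**The check largely exists.** SAP 7.3 already plans displays per visit, and SAP Table 26 gives limits over time. This stands in part: neither separates first from later series or is tied to this bias.

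**It comes late.** SAP 8.2 records an interim analysis after all subjects had completed V09, so changing access cannot repair V05 to V09 data. This stands.

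Three stronger readings are tempting, and the documents do not support them:
- A reader might attribute all 12 pairs at V06 to V09 (264 of 352) to home access. Eight of the 12 already follow same-visit ARGOS readings.
- A reader might infer that the limits shrink in direct proportion to the pull. That requires knowing the sensor value at that moment; the home database holds earlier values, and the four V05 pairs precede any home data.
- A reader might see a contradiction with CIP 4.6, which says "The data obtained by the ARGOS-IO system measurement will only be used for the evaluation of the trial outcome". That sentence restricts what the data are used for and leaves treatment decisions to GAT. It does not forbid viewing.

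**Conclusion.** The concern holds as a gap in observer masking. Both documents let investigators view home ARGOS values from V05 on, investigators take GAT, and the only safeguard works within a series. The gap newly reaches the first GAT reading at each of V06 to V09: 4 of 16 primary pairs per patient, 88 of 352 with 22 complete patients.

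The likely direction is toward flattering agreement. The size is unknown, and the documents do not show that any reading was affected. The conclusion rests on two assumptions: that those who read GAT are among the investigators with log-in rights, and that a reader who knows a patient's usual sensor level can be influenced by it.

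**What to change.** **Access.** Amend footnote 15 of CIP Table 6 and of SAP Table 1 so that the designated GAT readers have no access to home ARGOS data until the patient has completed V11. Other site staff keep access for device checks, including the check of the handheld reader at visits. The cost is a database permission setting. The small downside is that GAT readers cannot browse home profiles during the study. No treatment input is lost under the plan's own rule that only GAT guides care (CIP 4.6, 8.4.4.15). The change closes this route only: ARGOS values from the same visit and from earlier clinic visits may still be known.

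**Data already collected.** In SAP 7.3, report bias and limits for the first V05 series (22 pairs) beside those for the first series of V06 to V09 (88 pairs), as a sensitivity check. State that the comparison is confounded with post-surgical recovery and sensor drift. CIP 5.1.1.1 gives an initial bench drift below 3 mmHg per year; over days 30 to 180 that allows up to 3 × 150/365 = 1.2 mmHg from drift alone. The check can therefore flag a change but cannot attribute it. The cost is one additional table.

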4.3 Details about the manufacturer of the investigational device

The sponsor Implants Ophthalmic Products GmbH is the manufacturer of the implant and the Mesograph reading device. The implant injector is manufactured by DEUTSCHMANN INSTRUMENTS, Germany. The Multiline Connector to transfer the data from the reading device to a secure customized database via GSM technology, is manufactured by Medscale systems GmbH.

4.4 Device and accessories identification

Each ARGOS-IO pressure sensor implant will be identified by a unique 32-bit hexadecimal serial number stored in non-volatile memory on the ASIC. The reading device will be identified by a unique seven digit serial number.

4.5 Device accountability and storage

The investigational team at each site is responsible for ensuring investigational device accountability throughout the course of the study in accordance with regulatory requirements. Upon receipt of the devices, the investigator or designee will check for accurate delivery and acknowledge receipt by signing and dating the documentation provided by the sponsor. A copy of the receipt will be retained in the Investigator Site File.

Site staff will carefully record the serial number of each implant and reading device, as well as the ID number of the patient for which they were used, on the device accountability forms provided by the Sponsor. An accurate documentation of device accountability will be available for verification by the monitor at each monitoring visit. In addition, each patient will be given an implant pass identifying his/her device with type and serial number and listing further information including implantation date, sponsor contact information, implanting clinic and surgeon and warnings relevant to interactions with other medical procedures and devices as well as with metal detectors.

 Implandata Ophthalmic Products GmbH	Clinical Investigation Plan ARGOS-02	Revision C
		Page 35 of 106

Investigational device accountability records will include:

- Confirmation of Device delivery to the study site
- Device inventory at the site
- Device allocation to patients, including date of Device implantation, patient number and device identification number (serial number).

The sponsor's monitoring staff will verify that the study site's device accountability records match the records of used devices recorded in the CRFs.

The device must not be used for any purpose other than the present study. Unused devices will be returned to the sponsor at the end of the study period in accordance with the sponsor's instructions.

The investigator or authorized designee will alert the responsible monitor as soon as possible of any expected or potential shortage of devices during the study, so that the sponsor can organize the shipment of extra devices. Some extra devices will be provided in case any devices cannot be used.

The investigational devices must be kept in a secure place with restricted access. The shelf life of the device is 6 months under temperature conditions ranging from 0° C to +60° C.

4.6 Necessary training and experience requirements

It is assured that ophthalmic surgeons performing the surgery will be adequately trained on the ARGOS-IO pressure sensor implantation. Site personnel responsible for device handling including accountability, storage and shipment procedures will be trained during the initiation visit. If new site personnel are assigned during the study, they will be trained by the principal investigator or the monitor.

Surgical implantation

- Only specially trained ophthalmic surgeons may perform the implantation. These surgeons must be made familiar with the handling and implantation of the ARGOS-IO pressure sensor either by special training through Sponsor representatives or by consultation of the User Manual, provided as a separate document.

 Implandata Ophthalmic Products GmbH	Clinical Investigation Plan ARGOS-02	Revision C
		Page 36 of 106

Intraocular pressure measurement using the Mesograph Reading Device:

- Intraocular pressure (IOP) measurement may be carried out by any trained individual including patients and assistants. Health care professionals will be trained by sponsor representatives or their delegates. Trial staff will instruct patients on the use of the reading device for IOP self-measurement at home at visit 05. Patients will also be given separate written handling instructions provided by the Sponsor.

Setup of reading device, downloading of measurement data:

- Only specially trained site personnel may set up the reading device or download data from it. Special attention must be paid to maintaining data protection in this connection. Training will be provided by Sponsor representatives.

Evaluation of data:

- The data obtained by the ARGOS-IO system measurement will only be used for the evaluation of the trial outcome. The ophthalmologist will use only the IOP measurements made with GAT for diagnosis, therapeutic assessments and decisions about additional medical treatments.

4.7 Description of any specific medical or surgical procedures involved in the use of the investigational device.

Ophthalmic surgeons should perform the cataract surgery according to their local routine working procedures for cataract surgery. The implantation of the ARGOS-IO pressure sensor should occur according to the training received prior to any surgery given by the Sponsor.

Detailed implantation instructions are presented in the Instructions for Use (IFU) (Implandata Ophthalmic Products GmbH, 2014) and the Investigator's Brochure (IB) (Implandata, 2014).

 Impladata Ophthalmic Products GmbH	Clinical Investigation Plan ARGOS-02	Revision C
		Page 37 of 106

